4.4 Termination of the entire trial

Premature termination of the clinical trial will be considered when the risk-benefit ratio changes markedly for the patient, the use of the study medication is no longer justifiable, the sponsor believes it is necessary to terminate the clinical trial for safety reasons, when early evidence of the superiority or inferiority of a treatment group is obtained by an interim analysis after 25 and 50% of patients completed the trial, or by other research results, or when the clinical trial proves to be impracticable.

4.5 Unblinding

In the case of a requirement to unblind study medication, one of the chief investigators needs to be informed to discuss the unblinding. The unblinding list is held by the Institute of Medical Informatics, Statistics and Documentation (IMI), Medical University of Graz, which is not involved in study investigations.

5. VISIT PROCEDURES, MEASUREMENTS AND ASSESSMENTS

5.1 Recruitment and screening

Sites will recruit competitively and sites will receive compensation for their work based on a per-patient fee. The clinic staff of the EP/arrhythmia service informs patients about the possibility of being enrolled in this study. No study-related procedures are undertaken before obtaining informed consent. The study team in detail explains the study procedures and asks the participant about their willingness to participate in this research study. After informed consent is signed and obtained, participants are given a signed copy of the informed consent document and are assigned a screening identification number.

After obtaining informed consent at the screening visit, subject's eligibility will be further assessed and documented by using a source data form with a list of inclusion and exclusion criteria, medical history (including all medications past and current) will be acquired and the following measurements will be performed: body weight, height, blood pressure, ECG and blood parameters (see Table 2). Laboratory results up to 14 days before screening can be used to test eligibility for the trial.

Subjects unable to provide written informed consent will not be included in the study.

5.2 Randomisation

After screening, all eligible patients for the trial will be randomised into one of the two arms of the study via Randomiser Software (Institute for Medical Informatics, Statistics and Documentation, Medical University of Graz, <http://www.randomizer.at>), which will be programmed with a randomisation schedule provided by an independent statistician. The randomisation will be stratified by site, by type 2 diabetes and by eGFR < 60 vs \geq 60.

Only the subject number will be recorded in the case report form (CRF). The investigator will maintain a personal subject identification list (subject numbers with the corresponding subject names) to enable records to be identified.

A summary of all visits and procedures has been outlined below (Table 1). A more detailed description of each visit and accompanying procedures can be found later in the protocol (5.4 - 5.5)

confidential

5.3 Visit schedule

	Visit 1 (V1)	Visit 2 (V2)	Visit 3 (V3)
	Screening / Baseline	(Week 52 ± 4)	(4 weeks ±1w after V2)
Informed Consent	X		
Inclusion/exclusion criteria	X		
Randomisation	X		
Demography, medical history	X		
Concomitant medication	X	X	
Vital signs	X	X	
Height	X		
Weight	X	X	
Physical examination	X	X	
ECG	X		
Cardiac ultrasound	X	X	
Biobank sampling	X	X	
ICD interrogation	X	X	
nt-proBNP (local)	X	X	
Blood sampling	X	X	
Liver function parameters (AST, ALT, GGT)	X	X	
Renal function parameters (creatinine, eGFR)	X	X	
Adverse Events		X	X
Dispense medication	X		
Drug accountability		X	
Safety assessment before discharge	X		

Table 1: visit schedule (visit 3 telephone visit only)

5.4 Visit procedures

Visit 1 - Screening/Enrolment Visit (Day 0)

- Obtain informed consent of potential participant verified by signature on study informed consent form (10.5)
- Collect blood for routine biochemistry and to check inclusion criteria (eGFR, nt-proBNP) (5.5.5)
- Collect and prepare blood samples for biobank (5.5.6)
- Obtain demographic information, medical history, medication history and tobacco use history (5.5.1)
- Perform ECG, echocardiography, ICD interrogation (5.5.2)
- Record vital signs (5.5.3)
- Measure body weight and body height (5.5.4)
- Verify inclusion/exclusion criteria (4.1 and 4.2)
- Randomize the subject (5.2)
- Dispense the study medication for trial period (9.4)
- Adjust concomitant antihyperglycaemic medication
- Assessment of side effects and patient safety before discharge

Visit 2 - Follow-up Visit (Week 52 ± 4 weeks)

- Record adverse events as reported by participant or observed by investigator (6.1 – 6.5)
- Perform echocardiography, ICD interrogation (5.5.2)
- Record vital signs (5.5.3)
- Measure body weight (5.5.4)
- Collect blood for routine biochemistry (5.5.5)
- Record changes in medication (5.5.1)
- Collect and prepare blood samples for biobank (5.5.6)
- Record participant's adherence to treatment program
- Drug accountability (9.5)

Visit 3 - Telephone assessment (4 weeks ± 1 week after V2)

- Record adverse events as reported by participant (6.1 – 6.6)

5.5 Description of procedures and measurements

5.5.1 Medical history and physical examination

A medical history will be performed at the screening visit to record illnesses, disorders and medications. This information needs to be updated on all follow-up visits.

Physical examination will be performed at the Screening visit (study visit 1) according to local procedure. During this visit the physician will perform a physical examination with the focus on cardiac, lung and abdominal examination. Any abnormal, clinical significant findings must be recorded in the SDF (Source Data Form) as well as in the eCRF (HybridForms®). Any changes in subsequent visits as compared to the screening visit which fulfils the criteria of an AE must be recorded as an AE. Any changes in concomitant illness will be recorded as changes in medical history. Any changes in medications will be recorded in the eCRF.

5.5.2 ECG, echocardiography, ICD interrogation

An ECG, echocardiography, and ICD interrogation will be performed at the screening visit. In our study, ICDs are interrogated both with telemedicine (home-monitoring) and during on-site ICD follow-ups.

Patients will be offered to be included in our home-monitoring program. Currently, already 80% of patients have a home-monitoring device and routinely (every 4 months) transmit their data. In case of an alarm (sustained VT/VF) the data is transmitted automatically. In addition, all patients, regardless if they have a home-monitoring device or not, will be checked in the outpatient clinic on a yearly basis.

All arrhythmic events are recorded in the patient database. For this study, the number of episodes recorded during the study period will be tallied up.

All tests will be interpreted, signed and dated by the investigator before randomisation.

5.5.3 Vital signs

Pulse should be recorded at all visits after resting for five minutes in a sitting position. Systolic and diastolic blood pressure will be measured in sitting position at all visits.

5.5.4 Body weight and height

Weight should be measured at all visits. The same and calibrated pair of scales should preferably be used throughout the trial. Height will be recorded at the screening visit. BMI (body mass index) will be calculated as follows: $BMI = \frac{\text{weight (kg)}}{\text{height}^2 (m^2)}$.

5.5.5 Routine biochemistry

Blood samples will be obtained at all visits and processed by the local laboratory using standard methods' for routine tests. Patients can take their regular morning medications but are asked that they do not take any of their diabetes medications on the morning of their study visit. Patients should bring their regular medication along to their study visits to be further advised by the doctor. See table 2 below for a detailed description of blood collection at each visit:

Blood test	Visit 1	Visit 2
Haematology (full blood count)	X	X
HbA1c	X	X
Sodium, Potassium, Chloride	X	X
Calcium	X	X
Phosphate	X	X
Magnesium	X	X
Iron, Ferritin, Transferrin	X	X
Creatine Kinase	X	X
LDH (Lactatidehydrogenase)	X	X
AST (Aspartate-Aminotransferase)	X	X
CK MB	X	X
ALT (Alanine-Aminotransferase)	X	X
GGT (Gamma-Glutamyl-Transferase)	X	X
CRP (C-reactive Protein)	X	X
Creatinine	X	X
eGFR	X	X
Total cholesterol	X	X
Triglycerides	X	X
HDL (high density lipoprotein)	X	X
LDL (low density lipoprotein)	X	X
NT-pro BNP	X	X

Table 2: Summary of blood tests at each study visit

5.5.6 Blood sample collection and plasma extraction for biobanking

Blood will be collected via venous puncture into 16ml serum and 10ml EDTA vacutainers and centrifuged within 30 min of collection. Plasma should be transferred into Eppendorf tubes and stored at -80°C locally. In regular intervals these samples will be shipped on dry ice to the Biobank of the Medical University of Graz, where they will be stored at -80°C for future biomarker analyses. Additional biomarkers will be measured in batches from these stored biomarker samples.

5.6 Benefit-Risk Assessment

Ertugliflozin has been studied in subjects with type 2 diabetes as monotherapy as well as in combination with DDP-inhibitors as well as metformin. A cardiovascular safety study is ongoing(14). However, it has not been studied with respect to cardiac arrhythmias, yet. Other SGLT-2 inhibitors already finished the cardiovascular outcome trials(1; 15-17) demonstrating cardiovascular safety and beneficial effects, most prominent with respect to heart failure. A class effect can be assumed. Moreover, first data is published, demonstrating beneficial cardiovascular effects in non-diabetic patients with heart failure, too. As heart failure per se is a trigger for ventricular arrhythmias, every improvement in heart failure is likely to reduce ventricular arrhythmias, too.

With respect to diabetes it can be taken as given that the drug is not causing hypoglycaemic events per se, hypoglycaemia appears not to be a major issue in subjects without diabetes, that are studied in this trial as well. When ertugliflozin is used together with sulfonylurea or insulin, hypoglycaemia might occur and therefore participants will be instructed to reduce concomitant antihyperglycemic medication accordingly.

Fungal genital infections are the most common side effect of ertugliflozin and participants will be informed about this and instructed on prevention measures.

6. ADVERSE EVENTS (AE)

An AE is any untoward medical occurrence in a patient or clinical trial subject administered a medicinal product and which does not necessarily have a causal relationship with this treatment. An AE can therefore be any unfavourable and unintended sign (including an abnormal laboratory finding), symptom, including an exacerbation of a pre-existing condition, or disease temporally associated with the use of the trial device/procedure, whether or not considered related to the treatment.

All adverse events that occur during this study will be recorded on the adverse event case report forms.

6.1 Adverse Event description

For the purposes of the study, AEs will be followed up according to local practice until the event has stabilised or resolved, or the Follow-up Visit, whichever is the sooner. AEs will be recorded throughout the study.

6.2 Severity of Adverse Events

Mild: Awareness of event(s) or sign(s) but easily tolerated

Moderate: Discomfort enough to cause some interference with usual activity

Severe: Incapacitating or causing inability to carry out usual activity

6.3 Causality of Adverse Events

Medical judgment should be used to determine the relationship, considering all relevant factors, including pattern of reaction, temporal relationship, de-challenge or re-challenge, confounding factors such as concomitant medication, concomitant diseases and relevant history. Assessment of causal relationship should be recorded in the case report forms.

Yes: There is a reasonable causal relationship between the investigational product administered and the AE.

No: There is no reasonable causal relationship between the investigational product administered and the AE.

6.4 Abnormal Laboratory Test Results

All clinically significant abnormal laboratory test results besides creatinkinase and NT-proBNP occurring during the study will be recorded as adverse events.

6.5 Adverse events of Special Interest (AESIs)

The term AESI relates to any specific AE that has been identified at the project level as being of particular concern for prospective safety monitoring and safety assessment within this trial, e.g. the potential for AEs based on knowledge from other compounds in the same class. AESIs need to be reported to the Pharmacovigilance Department of MSD within the same timeframe that applies to SAEs.

Patients with AESIs need to be followed up appropriately, regardless of the origin of the laboratory data (e.g. central, local etc.). The Investigator should consider which, if any, concomitant therapies should not be taken during evaluation. Discontinued treatments can be reintroduced per Investigator discretion.

The following are considered as AESIs:

6.5.1 Hepatic injury

A hepatic injury is defined by the following alterations of hepatic laboratory parameters after randomisation:

- an elevation of AST and/or ALT ≥ 3 fold ULN combined with an elevation of total bilirubin ≥ 2 fold ULN measured in the same blood sample
- an isolated elevation of ALT and/or AST ≥ 5 fold ULN

These laboratory findings constitute a hepatic injury alert and the patients showing these abnormalities need to be followed up according to medical judgement.

In case of clinical symptoms of hepatic injury (icterus, unexplained encephalopathy, unexplained coagulopathy, right upper quadrant abdominal pain, etc.) without laboratory results (ALT, AST, total bilirubin) available, the Investigator should make sure these parameters are analysed, if necessary in an unscheduled blood test.

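### The combined hepatic-injury criterion in Protocol 6.5.1 needs total bilirubin, which no scheduled panel measures, so asymptomatic AST/ALT rises of 3 to below 5 × ULN at visit 2 cannot be classified

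*Protocol*

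**What the plan says.** - **Definition (Protocol 6.5.1).** The event is set by laboratory values: "A hepatic injury is defined by the following alterations of hepatic laboratory parameters after randomisation". Two criteria follow. The combined one is AST and/or ALT of at least 3 × ULN "combined with an elevation of total bilirubin" to at least 2 × ULN, with both values from one sample. The second is "an isolated elevation of ALT and/or AST ≥ 5 fold ULN". The word isolated shows that they are alternatives.
- **When more testing is called for (Protocol 6.5.1).** Patients who already meet a criterion are followed up as the investigator judges medically appropriate. A separate sentence covers symptoms: "In case of clinical symptoms of hepatic injury" where ALT, AST and total bilirubin results are not available, "the Investigator should make sure these parameters are analysed, if necessary in an unscheduled blood test".
- **Scheduled blood tests (Protocol 5.5.5, Table 2).** The table is introduced as the detailed account of what is collected at each visit. Its liver enzymes are AST, ALT and "GGT (Gamma-Glutamyl-Transferase"). Total bilirubin is not listed.
- **Schedules and safety lists.** The row in Protocol 5.3 reads "Liver function parameters (AST, ALT, GGT") and applies to visits 1 and 2. SAP 3.4 repeats it. Protocol 2.2 and SAP 2.2.3 list changes in the same three enzymes.
- **Reporting (Protocol 6.5 and 6.6.1).** AESIs go to the manufacturer on the timeline for serious adverse events: 24 hours or the next business day, whichever comes first.

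**The concern.** The protocol defines a laboratory alert and attaches fast reporting to it, but half of one of its two definitions rests on an analyte that the trial does not plan to measure. The renal AESI in Protocol 6.5.2 is built differently. It rests on creatinine, which is in Table 2 at both visits, and it orders an unscheduled creatinine sample when the alert occurs. The hepatic AESI has no equivalent for bilirubin, which suggests an oversight more than a choice.

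What is at stake is how a low count is read. If no combined-criterion event is reported, nobody can tell whether none occurred or whether bilirubin was not measured. A local laboratory may run bilirubin of its own accord, but nothing requires it, so ascertainment could vary by site.

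**Working it through.** The plan gives no figure to reproduce and no formula applies. The check sets the definition against every scheduled list and then works through the possible visit 2 results.

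**1. Is bilirubin planned anywhere?**

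| Place | Liver tests listed | Total bilirubin |
|---|---|---|
| Protocol 5.5.5, Table 2 (21 rows) | AST, ALT, GGT | no (0 of 21) |
| Protocol 5.3, Table 1 | AST, ALT, GGT | no |
| Protocol 2.2, safety objectives | AST, ALT, GGT | no |
| SAP 2.2.3, safety endpoints | AST, ALT, GGT | no |
| SAP 3.4, assessment schedule | AST, ALT, GGT | no |

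All five lists agree. Bilirubin appears only in Protocol 6.5.1.

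**2. Which scheduled samples can count?** The definition applies after randomisation. Visit 1 blood is drawn before randomisation and visit 3 is a telephone call (Protocol 5.3 and 5.4). That leaves one scheduled sample per patient, at visit 2 (week 52 ± 4).

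**3. What can be concluded from that sample?**

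| AST/ALT at visit 2 | Is bilirubin needed to classify? | Classifiable from the planned panel? |
|---|---|---|
| below 3 × ULN | no, neither criterion can be met | yes, not an AESI |
| 3 to below 5 × ULN | yes, it decides the combined criterion | no |
| 5 × ULN or more | no, an AESI whatever the bilirubin | yes, AESI |

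Only the middle row is open.

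**4. Does any other instruction close the middle row?**

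- With symptoms and no bilirubin result, the symptom sentence in 6.5.1 applies, so these patients have a route to testing.
- Without symptoms, that sentence does not apply. The follow-up sentence does not apply either, because it covers patients whose values already meet a criterion, and whether they do is what is unknown.

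The gap is therefore the asymptomatic patient with AST or ALT from 3 to below 5 × ULN at visit 2. The AESI is missed if that patient's bilirubin is in fact at least 2 × ULN.

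**5. Is the event lost altogether?** Protocol 6.4 requires clinically significant abnormal laboratory results to be recorded as adverse events, and Protocol 6.6 does the same for changes judged clinically relevant. The enzyme rise may therefore be on record. What can be missing is the AESI label and the reporting clock that goes with it.

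**The case against.** The strongest reply is that AESI work-up in this trial is event-driven, so absence from Table 2 proves little. The criteria for diabetic ketoacidosis in Protocol 6.5.3 use arterial pH, bicarbonate, ketones and plasma glucose, none of which is in Table 2. Protocol 6.5 also asks for follow-up whatever the origin of the laboratory data, so results from outside the study panel can count. This stands as far as it goes, but it does not close the gap. Work-up for ketoacidosis is prompted by how the patient presents. The combined hepatic criterion is a laboratory alert, and in a patient without symptoms nothing in the plan prompts the missing half of it.

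A second reply is that the gain is small: one additional look, at the end of treatment, with earlier detection left to unscheduled testing as now. That is true, and it limits the weight of the point. So does the fact that neither Protocol 2.2 nor SAP 2.2.3 lists hepatic injury as a safety endpoint in its own right.

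Three stronger readings are tempting, and the documents do not support them:

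- **That the trial cannot detect or count hepatic injury at all, or that its main criterion is lost.** The protocol ranks neither criterion above the other, and the 5 × ULN criterion can be assessed from planned tests.
- **That a later draw could never satisfy the same-sample clause.** The clause asks that both values come from one sample. It does not say that this must be the visit 2 tube. Any draw after randomisation that measures both would do. The weakness is only that no such draw is called for in asymptomatic patients.
- **That bilirubin at visit 1 is required.** The definition is relative to ULN and applies after randomisation, so a baseline value is useful for reference but not needed.

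**Conclusion.** The point holds in a limited form. In 0 of the scheduled samples can the combined criterion be assessed. The practical consequence falls on asymptomatic patients with AST or ALT from 3 to below 5 × ULN at visit 2, who may have an adverse event recorded but could miss AESI classification and expedited reporting.

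How many patients this concerns cannot be derived, because the documents give no rate for such enzyme rises or for raised bilirubin among them. Patients and physicians are blinded and randomisation is stratified by site, so the plan gives no reason to expect the omission to differ by arm. The likely effect is under-ascertainment, not a biased comparison.

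The conclusion assumes that Table 2 is the full list of planned tests, as its introduction suggests and the four other lists support. It also assumes that sites are under no separate instruction to run bilirubin. The primary endpoint, sample size and type I error are untouched. This is worth correcting because the remedy is specific and cheap.

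**What to change.** Reconcile Protocol 6.5.1 with Table 2:

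- Add total bilirubin to the visit 2 panel, run on the blood already drawn for routine biochemistry, and add it to the liver row of Protocol 5.3 and SAP 3.4. Visit 1 is optional, as a baseline reference.
- SAP section 7 records early termination, so some or all visits may be complete. For those, state in the SAP and the report that the combined criterion was not systematically assessed, and use whatever local bilirubin results exist.

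The thresholds and the management of patients stay as the protocol has them.

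The cost is one routine assay per patient, with no extra visit or venepuncture. On the 402 patients in the protocol synopsis that is at most 402 × 1 = 402 assays at visit 2, or 402 × 2 = 804 if visit 1 is included, and fewer after early termination. For completed visits the cost is a sentence in the SAP and the report, plus the work of retrieving local results.

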6.5.2 Decreased renal function

Decreased renal function is defined by a creatinine value showing a ≥ 2 fold increase from baseline and is above the ULN.

For the AESI “decreased renal function” the Investigator shall collect an unscheduled laboratory sample for creatinine as soon as possible and initiate follow-up laboratory tests of creatinine according to medical judgement.

6.5.3 Metabolic acidosis, ketoacidosis and diabetic ketoacidosis (DKA)

In case of metabolic acidosis, ketoacidosis and DKA further investigations should be done according to the medical judgment and the clinical course until a diagnosis is made and/or the patient is recovered.

DKA is defined by the diagnostic criteria in the table below, and as defined by the American Diabetes Association (ADA).

Investigators should note that not all criteria in the table below need to apply for the diagnosis of DKA, and clinical judgment should also be taken into consideration. Due to its mechanism of action, ertugliflozin may potentially modify the clinical presentation of DKA which may occur at lower plasma glucose levels than stated in the table below.

	DKA		
	Mild	Moderate	Severe
Plasma glucose (mg/dL)	>250	>250	>250
Arterial pH	7.25-7.30	7.00-7.24	<7.00
Serum bicarbonate (mEq/L)	15-18	10 to <15	<10
Urine ketones*	Positive	Positive	Positive
Serum ketones*	Positive	Positive	Positive
Effective serum osmolality (mOsm/kg)**	Variable	Variable	Variable
Anion gap***	>10	>12	>12
Alteration in sensoria or mental obtundation	Alert	Alert/drowsy	Stupor/coma

Table 3: Diagnostic criteria for DKA

* Nitroprusside reaction method

** Calculation: $2[\text{measured Na (mEq/L)} + \text{glucose (mg/dL)}]/18$

*** Calculation: $(\text{Na}^+) - (\text{Cl}^- + \text{HCO}_3^-)$ (mEq/L)

